## 6.2 Ascorbate Therapy

- 6.2.1 **Dose reductions** – As per Table 1 (below) if there is a DLT (Section 5.6)

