**Table 1. Phase 1b Dose De-escalation Schedule**

Number of Patients with DLT at a Given Ascorbate Dose	Decision Rule
$\geq 2$	Dose level will be declared toxic. If this is the lowest dose level, stop the study due to excessive toxicity; otherwise enter three additional patients at the next lowest dose level.
$\leq 1$ out of 3	Enter three more patients at this dose level.
$\leq 1$ out of 6	This is the recommended dose for the subsequent Phase2.

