## 6.3 Dose Limiting Toxicities

### Definitions of dose-limiting toxicity:

Toxicity will be evaluated according to CTCAE version 5.0. DLT will be defined as any of the following ascorbate related toxicity or related to the combination of pharmacologic ascorbate and radiation therapy during treatment and up to 28 days after the first pharmacologic ascorbate infusion:

- Infection grade 4
- SAE per 21CFR312.21 with an attribution of *possible, probable, or definite* to ascorbate
- Grade 3 diarrhea or nausea/vomiting despite maximal support
- Any grade 3/4 or greater hematologic or non-hematologic toxicity not explainable by another cause in the opinion of the principal investigator, with the exceptions of:
  - Expected radiation related skin toxicity of any grade.
  - Brief (< 1 week) grade 3 fatigue.

If unexpected DLT occurs, ascorbate administration should be delayed until the DLT has resolved to at least CTCAE version 5.0 grade 1 or baseline and future dose be reduced to dose level -1 as per table 1. If dosing is delayed by more than 4 weeks due to the occurrence of unexpected adverse event or if a patient already dose reduced to level -1 (62.5 gm/dose) experiences another DLT that is considered related to ascorbate, then the subject should be taken off study.

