## 8.4 Toxities

### 9. DIARRHEA, NAUSEA AND/OR VOMITING, KIDNEY STONES, DRY MOUTH/THIRST, HEADACHE, ABDOMINAL PAIN, FATIGUE, FACIAL FLUSHING, SWEATING, WEAKNESS, INJECTION SITE IRRITATION, AND FAINT/DIZZY (AFTER RAPID INFUSION), AND HYPERTENSION THAT MAY REQUIRE MEDICATION HAVE BEEN REPORTED. CORRELATIVE AND SPECIAL STUDIES

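### The within-patient dose-reduction rule has two different triggers, points to a cohort table, and gives no workable action for a first DLT in a patient who started at Dose -1

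*Combined protocol and SAP*

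**What the plan says.** Section 5.6.6 sends the reader to Section 6.2 for dose modifications. There, 6.2.1 gives the rule for dose reductions as "As per Table 1 (below) if there is a DLT (Section 5.6", with no limit on the kind of DLT.

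Section 6.3 defines DLTs and then adds a patient-level rule of its own: "If unexpected DLT occurs, ascorbate administration should be delayed until the DLT has resolved" to grade 1 or baseline, with the "future dose be reduced to dose level -1 as per table 1". The subject leaves the study if dosing is delayed more than 4 weeks because of an unexpected adverse event, or "if a patient already dose reduced to level -1 (62.5 gm/dose) experiences another DLT that is considered related to ascorbate".

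Table 1 in Section 6.2 repeats the Phase 1b schedule of Section 5.2. Its first column is "Number of Patients with DLT at a Given Ascorbate Dose". At two or more, the level is declared toxic and the table continues: "If this is the lowest dose level, stop the study due to excessive toxicity; otherwise enter" three further patients at the next lowest level. Section 12.1 likewise assigns the next cohort to Dose -1.

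Two other places bear on this. The toxicity list at Section 8.4 begins "DIARRHEA, NAUSEA AND/OR VOMITING, KIDNEY STONES, DRY MOUTH/THIRST" and gives no grades. Section 7.3 defines *unexpected* for FDA reporting.

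**The concern.** These passages tell the treating physician what to do after a dose-limiting toxicity, in a study whose Phase 1b objective is safety and tolerability. Two physicians who both follow the protocol could act differently after the same event, one under 6.2.1 and the other under 6.3. The table cited to settle the matter does not address a treated patient. If the Dose -1 cohort opens, its patients have no stated action after a first DLT that can be carried out.

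What is at stake is consistent handling of patients after a DLT and, secondarily, knowing what dose was given afterwards. The DLT count that selects the Phase 2 dose is not affected, because a first DLT is counted when it occurs.

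**Working it through.** The plan states no DLT rate and no probability on this point, so there is no figure to reproduce. The check is mainly a comparison of text.

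**Trigger**

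| Source | Condition | Action | Unit |
|---|---|---|---|
| 6.2.1 | any DLT | reduce, citing Table 1 | patient |
| 6.3 | *unexpected* DLT | delay, then reduce to Dose -1, citing Table 1 | patient |
| Table 1 (5.2, 6.2); 12.1 | two or more patients with a DLT at a level | next patients enter one level lower, or stop | cohort |

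The first two rows set different conditions for the same patient-level action, and 6.3 is silent on a DLT that is not unexpected. The third row concerns a different decision.

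**Where the two triggers can diverge.** Section 6.3 names grade 3 diarrhea or nausea/vomiting that persists under full supportive care as a DLT. Section 8.4 lists the same symptoms as reported toxicities. If a listed symptom is an expected one, 6.2.1 reduces the dose and 6.3 does not apply. If the 7.3 definition is borrowed, an event is also unexpected when it is not listed at the severity observed. Since 8.4 gives no grades, a grade 3 event could then fall within 6.3. The documents do not choose between these readings, and 6.3 does not cite 7.3.

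**Cross-references.** Section 6.2.1 cites 5.6 for DLTs, but DLTs are defined in 6.3, and 5.6.6 refers back to 6.2. The label Table 1 is used for four tables (the Schema, 5.2, 5.6 and 6.2). The Schema version has different decision rules, and the 5.6 version lists infusion times.

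**First DLT in a patient who started at Dose -1**

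1. Such patients can exist under Table 1 and 12.1. Against that, 5.6.1 and the note under the dose-level lists give every patient 75 gm, and 5.3 places Phase 2 at Dose 0.
2. Section 6.3 offers one reduced dose, 62.5 gm, which this patient is already receiving.
3. The off-study clause needs a patient who has already been reduced and who then has a further DLT. Neither condition is met.
4. What remains is the clause on delays over 4 weeks, in a course of about 5 weeks (12.1), and Section 5.9, under which treatment may be stopped for unacceptable adverse events.

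**How often this could matter.** Let p be the DLT rate. It is assumed, taken as equal at both doses, with independent patients.

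- A = P(exactly 1 of 6 at Dose 0) = 6p(1−p)^5. The cohort stays at Dose 0 and only the patient-level rule is in play.
- B = P(at least 2 of 6) = 1 − (1−p)^6 − 6p(1−p)^5. Dose -1 opens. Entering patients in two groups of three does not change B, because two DLTs among the first three are already two among six.
- C = P(at least 1 DLT among the first 3 at Dose -1) = 1 − (1−p)^3.

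| p | A | B | C | B × C |
|---|---|---|---|---|
| 0.10 | 0.354 | 1 − 0.531 − 0.354 = 0.114 | 1 − 0.729 = 0.271 | 0.03 |
| 0.20 | 0.393 | 1 − 0.262 − 0.393 = 0.345 | 1 − 0.512 = 0.488 | 0.17 |
| 0.30 | 0.303 | 1 − 0.118 − 0.303 = 0.580 | 1 − 0.343 = 0.657 | 0.38 |

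B is only the chance that Dose -1 opens. B × C is an illustration for the first three Dose -1 patients, before the 4-week clause or 5.9 is considered.

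**The case against.** The strongest reply is that these are drafting slips in a protocol that leaves room for judgment. Section 6.2.1 already covers every DLT, and 6.3 never tells anyone to continue treatment. Section 5.9 allows ascorbate to be stopped. The pointer to Table 1 may mean the dose-level list printed directly beneath it. Under the full 7.3 definition, grade 3 diarrhea may well be unexpected: Section 1.3 describes only minor events, including diarrhea, in one ascorbate study and no toxicity of grade 3 or above in another. The two triggers might then agree.

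Much of this stands, and it rules out several stronger readings that a reader might infer:

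- *Three conflicting within-patient triggers.* Not supported. The two-patient criterion is a cohort rule and can coexist with a patient-level rule.
- *Section 6.3 sends a Dose -1 starter back to the dose at which the DLT occurred.* Not supported as an instruction. A reduction to Dose -1 cannot be carried out for someone already there. The text leaves a gap, and treatment can still end under the 4-week clause or 5.9.
- *Some patients would be continued at full dose.* No passage says so.
- *Every listed toxicity falls outside 6.3.* Not established, for the severity reason above.

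The objection does not remove the core. The conditions in 6.2.1 and 6.3 differ on their face, and 6.3 does not define its own qualifier. Reading the pointer as the dose-level list supplies a dose but no patient-level rule. Section 5.9 is discretionary, and a delay of more than 4 weeks can rarely arise within a course of about 5 weeks.

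**Conclusion.** The point holds as an internal inconsistency in a patient-safety rule. There are two differing patient-level triggers, a shared pointer to a table with no within-patient instruction, a wrong section reference, and no workable stated action for a first DLT in a patient who started at Dose -1.

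The trigger conflict does not depend on Dose -1 opening. It depends on a DLT occurring that one reader would call expected. The Dose -1 gap requires that cohort to open (0.11, 0.34 or 0.58 at assumed DLT rates of 10%, 20% or 30%) and then a DLT in a patient who started there. Those three figures should not be read as the chance that a patient meets the gap. Nor should the 6 patients at a level in Phase 1b, or the 25 at the RP2D, be read as patients affected; they are enrolment counts. No effect on the pCR analysis is shown.

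**What to change.** - Reconcile 6.2.1, 6.3 and Table 1 so that one trigger governs within-patient dose modification. If *unexpected* is kept, define it in 6.3 and state what happens after other DLTs.
- Correct the reference in 6.2.1 from Section 5.6 to 6.3.
- Separate the within-patient rule from the cohort table, under its own label, and number the four tables now called Table 1 distinctly.
- Reconcile the statements that everyone receives 75 gm (5.6.1 and the dose-level notes), and the Phase 2 dosing in 5.3, with the Dose -1 cohort in Table 1 and 12.1.
- State the action after a first DLT for each starting dose.

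Which trigger applies, and which clinical action follows for each starting dose, is for the sponsor to decide; this review takes no position on either. The cost is protocol wording and one small table, with no extra patients, procedures or change to the sample size.

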## 5.6 Concomitant Ascorbate (High-dose Ascorbic Acid) Infusions

5.6.1 **Participant dose.** All patients will receive a standard ascorbate dose of 75 gm given over 120 minutes

5.6.2 **Administration.** Based on subject tolerance; infusion rate should not exceed 500 mL/hour without consulting with physician. Recommended infusions times are as follows (Table 1) but may be adjusted for subject comfort. Changes in infusion rates should be recorded.

5.6.3 **Initiation.** Start the week prior to chemoradiation with one 15-g infusion. This is the test dose. 75 gm dosing begins week 1 of radiation therapy. If the participant fails the 15g test dose it is not considered dose limiting toxicity.

5.6.4 **Schedule.** Scheduled three times weekly during chemoradiation;

5.6.5 **Duration.** Subjects will continue with therapy until the end of standard radiation therapy or if any criteria of removal are met (Section 5.7)

5.6.6 **Dose modifications.** Provided in Section 6.2

**Table 1.** Recommended Infusion Times for Pharmacological Ascorbate †

Ascorbate dose (500 mg / mL)	Total volume*	Osmolarity (mOsm/L) §	Infusion Time
15g (30 mL)	250 mL	681	30 minutes
75g (150 mL)	1000 mL	851.7	120 minutes
62.5 g (125 mL)	1000 mL	709	120 mins

† Provided by Drug Information Center at the University of Iowa, July 2011

\* Sterile water for injection only. Do not use D5W

§ Theoretical calculations provided by Drug Information Center; targeted osmolarity range is 500 – 900 mOsm/L

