## 5.9 Criteria for removal from study

Treatment with pharmacological ascorbate may be discontinued if any one of the following criteria is met:

- Intercurrent illness that prevents further administration of treatment,
- Unacceptable adverse event(s),
- Patient decides to withdraw from the study, or
- General or specific changes in the patient's condition render the patient unacceptable for further treatment in the judgment of the investigator
- Progressive disease as determined by the investigator
- A female subject becomes pregnant or fails to use 2 highly effective methods of contraception (for those subjects who are able to conceive).
- A female subject breast feeds while on study treatment.
- A male subject fails to use a highly effective method of contraception

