## 10. STUDY CALENDAR

### 10.1 Study Procedures

	Screen b	Treatment a					Off treatment and end of study c	Follow Up d
		Week 1	Week 2	Week 3	Week 4	Week 5 (+1wk j )		
H & P	X	X		X		X		
Tumor biopsy (optional)	X b							
Performance status	X						X	X
Clinical MRI/ Staging CT	X						X	X e
Pregnancy test k (urine)	X							
G6PD	X							
EKG	X							
CBC w/diff	X			X		X		
PT/INR, PTT & uric acid	X							
Height	X							
Weight, BSA	X						X	
Vitals (BP, pulse) m	X	X	x	X	x	X	X	
Comprehensive metabolic panel (CMP)	X	X		X		X	X	
Ascorbate infusion	X i	XXX	XXX	XXX	XXX	XXX		
Blood for ascorbate levels f	X	X		X		X		
ROS Research blood g	X	X		X		X	X	
Immunology research lab g	X					X	X	
Iron Panel including ferritin h	X						X	
T2* /QSM and DWI MR imaging sequences (optional)	X			X			X	
Adverse Events & Con Meds			X	X	X	X	X	

**a** study day 1 is defined as radiation therapy day 1 (i.e., fraction 1).

**b** screening labs, history, and physical must be obtained  $\leq$  28d from d1. G6PD may be obtained at any time prior to test dose. MRI/CT obtained  $\leq$  28d from d1 (RT sim is acceptable). Pregnancy test per institutional guidelines. Optional tumor biopsy can be done anytime before week 1 dosing.

**c** includes both off-treatment evaluation and study completion. Study completion requires a final study dictated visit 4 to 6 weeks after the last dose of ascorbate. Follow at least monthly until resolution of all ascorbate related adverse events.

**d** approx every 3 months (every 12 weeks [+/- 4 weeks]) for overall survival through passive chart review, phone call or scheduled follow-up visit for 2 years

**e** Imaging as per standard of care for site specific sarcomas

**f** 4cc green-top Na-Heparin tube. Draw pre-infusion at 15g dose, then 30 min post-infusion: week 1 day 1 , week 3 and last infusion of week 5

**g** 6cc pink-top EDTA tube. Draw pre infusion The specimen should be placed on ice immediately after draw and carried to the lab

**h** At time of screening and end of study

**i** Test dose of 15 g intravenously once G6PD levels confirmed to be adequate. A physician must review the patient's medication list against the list of medications prohibited on this trial prior to the test dose of ascorbate.

**j** In case of radiation treatment delays due to holidays

**k**  $\pm 7$  days prior to day 1

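### Section 6.3 takes some subjects off study for ascorbate toxicity, and nothing separates stopping ascorbate from leaving the study, so treated subjects could be selectively lost to pCR, TTP and OS

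*Combined protocol and SAP*

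**What the plan says.** Four places in the protocol bear on what happens when ascorbate stops.

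- **Section 6.3** has two triggers for leaving the study. One begins "If dosing is delayed by more than 4 weeks due to the occurrence of unexpected adverse event". The other applies to a subject already reduced to level -1 who "experiences another DLT that is considered related to ascorbate, then the subject should be taken off study".
- **Section 5.9** is headed "Criteria for removal from study", but its operative sentence reads "Treatment with pharmacological ascorbate may be discontinued if any one of the following criteria is met". Its list mixes treatment reasons, such as unacceptable adverse events and investigator-judged progression, with the patient's own decision to withdraw from the study.
- **Section 5.6.5** lets ascorbate run to the end of radiation "or if any criteria of removal are met (Section 5.7". Section 5.7 holds the radiation rules and contains no removal criteria.
- **Section 10.1** has a single calendar column for off treatment and end of study. Footnote c says that it "includes both off-treatment evaluation and study completion" and adds "Follow at least monthly until resolution of all ascorbate related adverse events". A separate follow-up column (footnote d) then runs for 2 years.

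Sections 5.10 and 10.3 describe about 2 years of follow-up after surgery and are silent on subjects taken off study. Section 12 gives no rule for such subjects in the pCR, TTP or OS analyses.

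**The concern.** Stopping a study drug and leaving a study have different consequences for the data. A subject who stops ascorbate here will usually still produce the endpoints. Section 5.7 describes the radiation as the institution's standard pre-operative treatment, also given outside the protocol. Section 6.1.1 leaves the radiation dose unmodified, and Section 5.1 places surgery 4 to 6 weeks after radiation. A resection specimen, recurrence status and survival status would normally exist.

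If 6.3 is applied literally, those data need not be collected, and the reason for the loss is toxicity. In a single-arm trial of 25, the pCR rate would then lean towards subjects who tolerated the combination, and the Kaplan-Meier estimates would lose people for a reason connected with treatment. Each subject is 1/25 = 4% of the cohort.

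**Working it through.** **Inputs.** Section 12.2 gives n = 25, a null pCR rate of 10%, an alternative of 30%, a one-sided exact binomial test, success at 6 or more responders, power of 81% and an achieved level of 0.03. The documents give no removal rate, so the number removed below is an assumption.

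**1. The plan's own figures.** With X ~ Bin(n, p), the chance of success is P(X ≥ 6) = Σ C(n,x) pˣ (1−p)ⁿ⁻ˣ, summed from x = 6 to n.
- n = 25, p = 0.30: 0.8065, which matches 81%.
- n = 25, p = 0.10: 0.0334, which matches 0.03.

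**2. Subjects lost, not replaced, cut-off of 6 kept.** If k subjects are lost, power is P(Bin(25−k, 0.30) ≥ 6).

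**3. The same subjects kept, but responding at 10%.** Subjects who stop early have had less ascorbate, so 30% may be too high for them. Assuming the radiation-alone rate of 10% for those k subjects, power is P(Y + Z ≥ 6), with Y ~ Bin(25−k, 0.30) and Z ~ Bin(k, 0.10).

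| k | Lost (step 2) | Kept at 10% (step 3) | Gain from keeping |
|---|---|---|---|
| 1 | 0.771 | 0.783 | 0.012 |
| 2 | 0.731 | 0.757 | 0.026 |
| 3 | 0.687 | 0.730 | 0.043 |

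If the removed subjects would never respond, keeping them changes power by nothing. If they would respond at 30%, keeping them restores the full 0.807.

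**4. Subjects lost and replaced to reach 25.** As a worst case, suppose that the true rate among all treated subjects is 10%, a fraction f is removed, and every removed subject would be a non-responder. The rate among those left is 0.10/(1−f), and the type I error of the 6-of-25 rule is P(Bin(25, 0.10/(1−f)) ≥ 6).

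| f | Rate among those left | Type I error |
|---|---|---|
| 4% | 0.1042 | 0.0397 |
| 8% | 0.1087 | 0.0475 |
| 12% | 0.1136 | 0.0570 |
| 16% | 0.1190 | 0.0687 |
| 20% | 0.1250 | 0.0831 |

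The 0.05 target is passed between 8% and 12% removal.

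**5. Timing.** Ascorbate is planned for 5 weeks (Sections 10.1 and 12.1). A delay of more than 4 weeks that starts after the first week's dosing cannot be reached before about week 5, when radiation is nearly or fully delivered. That trigger therefore falls shortly before the surgery that supplies the primary endpoint.

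**The case against.** The strongest reply is that the protocol's end-of-study language does not end follow-up. In the calendar every subject passes through study completion 4 to 6 weeks after the last ascorbate dose and is then followed for survival for 2 years, by chart review if need be (footnote d). Section 11.1 has all resected samples reviewed, and Section 12.3 counts patients treated at the recommended dose. No section writes an exclusion of these subjects from any analysis. This stands: the loss is possible, not prescribed. It does not settle the matter, because 6.3 directs removal and nothing says that the calendar's follow-up or the pathology read survives it.

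Several stronger readings are tempting and are not supported:

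- *Any ascorbate toxicity removes a subject.* A first DLT leads to delay and dose reduction. Only the two triggers in 6.3 remove, and the delay trigger does not require attribution to ascorbate. Both must arise around a course of about 5 weeks, and the earlier ascorbate trials described in Section 1.3 report little toxicity, so few subjects may be affected.
- *Progressing subjects are removed.* Progression appears only in 5.9, whose text stops ascorbate and not participation. A subject with documented progression has also already had the TTP event.
- *Toxicity follow-up becomes impossible.* Footnote c places monthly follow-up in the very column that marks study completion, and Section 7.5 and Appendix D carry event recording through 30 days after treatment.
- *The 10% benchmark is free of any such selection.* The documents do not describe the denominators behind it.
- *The full drop in power is recoverable.* That holds only if removed subjects would respond at 30%. At 10%, the gain is about 0.01 to 0.04.

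**Conclusion.** The concern holds as a risk of selective loss that the text permits. Section 6.3 gives a rule that, read literally, takes treated subjects out of the study for toxicity. Section 5.9 does not agree with its own heading, 5.6.5 points to the wrong section, the calendar merges two different events, and no section protects the endpoint data.

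The size is unknown. With 1 to 3 of 25 lost and not replaced, power is 0.77 to 0.69 against the planned 0.81; if those subjects would respond at 10%, retaining them gives 0.78 to 0.73. Under replacement and the worst-case assumption of no responders among those removed, the type I error exceeds 0.05 somewhere between 8% and 12% removal. All of these figures rest on assumed removal counts and assumed response rates in the removed subjects. The main issue is which subjects the estimates describe; the change in power is secondary.

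**What to change.** Reconcile Sections 6.3, 5.9, 5.6.5 (with its cross-reference) and calendar footnote c, so that stopping ascorbate and leaving the study are separate events with separate criteria. Which events stop ascorbate, and when, is for the sponsor to decide.

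Then state the data rule. Treated subjects who stop ascorbate keep the pathology read, the pre-operative imaging, adverse-event follow-up, and progression and survival follow-up. They stay in the pCR, TTP and OS analyses unless they withdraw consent.

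The cost is amendment wording, since most of these data already arise from standard care. The small downside is that subjects with low ascorbate exposure remain in the pCR rate and may lower it slightly.

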## 7. ADVERSE EVENTS: LIST AND REPORTING REQUIREMENTS

This study will also be monitored by internal oversight specialists at the University of Iowa. *The Data and Safety Monitoring Plan of the Holden Comprehensive Cancer Center* provides standard operating procedures to monitor all clinical cancer trials at the UIHC. All investigator-initiated trials are automatically monitored by the Data and Safety Monitoring Committee (DSMC). A detailed data and safety monitoring plan for this study is provided (Appendix). This study has been assigned as a risk level 4 as it utilizes an investigator sponsored IND.

